The aims of this study are to identify the impacts of personalized nature-based Tandem VR experiences on the quality of life, pain, and fear of death in patient-caregiver dyads enrolled with **hospice services** and determine the acceptance of a personalized nature-based Tandem VR experience by hospice teams as a non-pharmacological modality for addressing needs of dyads. Our study will use a synchronized Tandem VR approach where patient-caregiver dyads wear a head-mounted display presenting immersive nature-based content. This **mixed methods study** will recruit **20+ patient-caregiver dyads** from **Prisma Health Hospice of the Foothills** enrolled in home hospice services nearing the end of life. Self-reported outcomes will be collected before and after the 5–15-minute intervention. Our objectives are to assess the effectiveness of Tandem VR on patient reported outcomes including quality of life, pain, and fear of death, and acceptance of the Tandem VR intervention in the home setting. If successful, this study will introduce a treatment incorporating patient-caregiver dyads to help reduce symptomatology and improve quality of life.

II. INTRODUCTION

A. BACKGROUND

Nature-based virtual reality (VR) experiences in head-mounted displays (HMDs) offer powerful, non-pharmacological tools for hospice teams to help patients undergoing end-of-life (EOL) transitions.¹ Being outdoors in natural environments can activate the parasympathetic nervous system and brain regions associated with physiological relaxation.² Evidence suggests that nature-based VR experiences can have similar effects³, thereby reducing the symptom burden in physical and psychological domains.^{4,5} These symptoms negatively impact functional status, leading to isolation, loneliness, and poor quality of life (QOL).^{6,7} In a recent study by [name], [name], [name]... [name] & [name] (under review), patients with end-stage Chronic Obstructive Pulmonary Disease (COPD) showed improvements in shortness of breath and comfort during a personalized nature-based VR experience.⁸

Implementing nature-based VR allows patients to feel present as if they were genuinely standing in outdoor environments without the challenges of leaving their homes.⁹ Personalizing these VR experiences allows patients to revisit familiar and non-threatening spaces where memorable experiences occurred.^{10,11} Implementing such a personalized, technologically-advanced intervention among patients enrolled in hospice is expected to significantly mitigate stressors associated with serious illness and EOL events by bringing joy and closure at the end of their lives.¹²

Patients are not the only individuals in the hospice setting who can benefit from nature-based VR experiences. Informal caregivers, such as a spouse, partner, or friend, play crucial roles in hospice patients' physical, emotional, and practical care. On average, these caregivers deliver an estimated 66 hours per week of care and are intimately involved in the EOL phases.¹³ Providing this amount of care requires significant physical and emotional sacrifices. Caregivers' own health often deteriorates as the burden and strain of caregiving increases.¹⁴ The psychological distress of the patient-caregiver dyad is interconnected and highlights the interdependence and responsiveness to distress as a unit.¹⁵ While caregivers survive beyond the patient, reducing their physical and psychological impact offers long-term benefits in their well-being and bereavement process.¹⁶ What is currently missing from hospice care services and this public health issue is a strategy to help reduce burnout and the impact of caregiving on informal caregivers. Therefore, the use of simultaneous personalized nature-based VR, or Tandem VR, experiences may provide the needed strategy for the well-being of the dyad by allowing them to engage in meaningful experiences simultaneously.

Dyads have missed opportunities to engage in meaningful experiences, given the progressive nature of serious illnesses. Events such as family gathering for picnics or hiking in familiar outdoors spaces often hold valuable memories. The images, videos, and sounds can be personalized in nature-based VR experiences for use by each dyad. In Tandem VR, the dyad experiences memorable nature experiences concurrently. They can interact during the experience to recall precious moments or joyful times. Providing stimuli of sights and sounds, panoramic views with high resolution, and allowing interaction are key components in distraction techniques that can reduce the symptom burden during EOL phases. Evidence supports the use of distraction techniques through VR experiences, with one

study reporting a 30-50% reduction in pain scores.¹⁶ The uptake of Tandem VR by hospice teams offers a person-centered strategy for the patient’s wellbeing and the psychological needs of informal caregivers.

B. IMPORTANCE / JUSTIFICATION FOR STUDY

The primary objective of this study is to assess the impact of personalized nature-based Tandem VR experiences on QOL, pain, and fear of death in patient-caregiver dyads enrolled in hospice services.

Additionally, the study will determine the acceptance of personalized nature-based Tandem VR experiences by hospice teams as a non-pharmacological modality for addressing the needs of dyads.

Ongoing and statistically significant research show that VR experiences, interventions, and meditations can significantly lower patients' physical pain, anxiety, and depression levels and reduce medication use. Using personalized, nature-based VR experiences, the patient-caregiver dyads can simultaneously engage in an immersive encounter to help alleviate symptoms associated with declining health and EOL phases. Preliminary data on using Tandem VR for patients with serious illnesses demonstrate a positive impact by reducing pain and anxiety while allowing the dyad to reconnect in a peaceful, nature-based environment ([name] et al., under review). A growing body of evidence on the value of VR for patients with serious illnesses supports this innovative approach and positions the proposed research at the forefront of scientific and clinical transformative care. Our team is committed to investigating this therapeutic modality for patients and their caregivers by providing an experience that is comforting, peaceful, and practical in its implementation. The study further extends the need for person- and caregiver-centered, non-pharmacological interventions to reduce physical, psychological, and spiritual distress. Inspired by Prisma Health's mission to transform the healthcare experiences for patients and families, the Tandem VR intervention helps patients and their caregivers dealing with EOL concerns. Our team is committed to inspiring a new treatment modality, providing patients with an experience that is inspiring, respectful, and practical in its implementation. The project extends the need for person-centered outcome measures of symptom burden, an area in which additional research is needed.

III. HYPOTHESIS & OBJECTIVES

A. HYPOTHESIS

Patients transitioning to EOL have declining functional status, limiting their participation in meaningful moments and experiences. The loss of physical strength and increasingly burdensome symptoms prevent them and their caregivers from engaging in personal and profound "Bucket List" items, such as outdoor excursions. Many of these individuals require significant help from a spouse, family member, friend, or neighbor with activities of daily living (ADLs), medication management, and other household needs. These informal, unpaid caregivers often experience stressors in the role and develop physical and mental health issues (Adashek & Subbiah, 2020).

Informal, unpaid caregivers (CGs) are defined as a relative, possibly a spouse or partner, friend or neighbor, who supports the broad range of needs of the patient (Jacobs et al., 2022). The care may often include financial and legal support (Li et al., 2018). Nearly 66 million Americans serve as CGs (National Alliance for Caregiving & American Association of Retired Persons, 2015).

Providing the necessary care creates financial issues and social isolation (Faronbi, Faronbi, Ayamolowo, & Olaogun, 2019). With CGs being the primary source of care, the annual estimated loss of income is \$522 million, and replacing these with unskilled paid care at minimum wage would cost \$221 billion a year (Chari, Engberg, Ray, & Mehrotra, 2015). As a dyad, they may be bound to the home for extended periods without reprieve from outside sources. As social isolation continues, physical and psychological issues become exacerbated (Donovan & Blazer, 2020).

VR is a cutting-edge technology increasingly used by palliative care and hospice organizations worldwide to help bring meaning, joy, healing, and closure to many patients at the end of their lives (Carmont & McIlpatrick, 2022). This technology includes a VR headset that patients wear over their eyes, providing a complete, 360-degree, immersive virtual experience. An example of the benefit of this technology is a patient who has dreamed of visiting another country but cannot leave their bed due to sickness, frailty, and weakness. An immersive VR experience brings distance

areas to the patient at the bedside and helps them complete unreachable locations while providing existential closure.

The experience can also be shared through Tandem VR. In this environment, not only does the patient get to visit another place where they have never been, the caregiver can go with them. The dyad is joined via two headsets controlled by a central laptop or tablet device to project the same videos and imagery into the experience simultaneously. The dyad can communicate openly to each other, especially their emotions from the interaction. Personalizing the experience for the dyad also helps them to see a place that feels authentic to them, allowing them to feel a part of the environment without having to navigate the challenges of travel. The novel concept of Tandem VR provides a strategy to develop person-centered care simultaneously with the caregiver to relive or create meaningful experiences.

We propose an innovative, mixed-methods study to test the impact and acceptance of Tandem VR in the hospice home setting. This study seeks to: (1) Identify the impacts of personalized nature-based Tandem VR experiences on the QOL, pain, and fear of death in patient-caregiver dyads enrolled with hospice services. (2) Determine the acceptance of personalized nature-based Tandem VR experiences by hospice teams as a non-pharmacological modality for addressing the needs of dyads. This study will recruit 20+ patient-caregiver dyads from Prisma Health Hospice of the Foothills, who be receiving the Tandem VR intervention from Research Recruiters implementing the treatment modality. The Research Recruiters, Prisma Health social workers and Tandem VR research team members, will screen, determine eligibility with the research team, implement, and evaluate the use of the Tandem VR intervention with patient-caregiver dyads. The study will collect patient-caregiver reported outcomes including quality of life, pain, and fear of death. The investigators will also measure acceptability and impact of exposure to Tandem VR. The investigators will also collect qualitative data following participants' Tandem VR experience to better understand patient and caregiver preferences, thoughts, and feelings about the intervention. Outcomes will be measure before and after the intervention. We expect that this study will demonstrate Tandem VR

is an effective non-pharmacologic treatment for improving QOL at EOL and will be acceptable and safely deployed in the home settings.

Since the treatment is administered via technology at home, barriers associated with a clinical environment (such as noise, time, patient accessibility) are not impediments to the treatment. This consistency of treatment combined with the use of validated symptoms assessment scales will provide our study with excellent methodological quality. If successful, this data will be used to optimize Tandem VR and enable us to apply for external funding involving a larger population of hospice patients. The results will also inform best practices for the implementation of Tandem VR for patient-caregiver dyads in hospice care.

B. OBJECTIVES

The primary aim of this study is to measure the impact on QOL using Tandem VR with patient-caregiver dyads transitioning to EOL. Our study will utilize an approach where participants will be asked to wear a VR HMD presenting Tandem VR content in a home setting. In addition to measuring the improvement in QOL, this study seeks to assess the efficacy of Tandem VR on patient-caregiver reported outcomes including pain and fear of death and assess the acceptability and safe use of Tandem VR in a home setting. The study will recruit 20+ patients from Prisma Health Hospice of the Foothills, who will be enrolled for treatment with Tandem VR. Research Recruiters will assist eligible patient-caregiver dyads in using the Tandem VR intervention in the comfort of their own home. The objective is to gather data on patients transitioning to EOL after being exposed to Tandem VR. The study will collect patient-caregiver reported outcomes including QOL, pain, and fear of death. The investigators will also assess acceptability and safety of Tandem VR at home. The investigators will also collect qualitative data following participants' Tandem VR experience to better understand the dyads' preferences, thoughts, and feelings about the intervention. Qualitative data will be garnered through audio recording in Otter, direct observation, and an interview. Outcomes will be measured before, and after the intervention. We expect that this study will demonstrate Tandem VR is an effective

non-pharmacologic treatment for improving QOL at EOL in patient-caregiver dyads; moreover, we expect Tandem VR will be acceptable and safely deployed in home settings.

IV. DESIGN & METHODS

A. STUDY DESIGN

Mixed-methods interventional study design: The study will recruit 20+ patient-caregiver dyads from Prisma Health Hospice of the Foothills enrolled in home care or at the hospice house. Once recruited, the dyads will be screened using the inclusion and exclusion criterion to ensure study eligibility. Dyads will also be offered the opportunity to participate in the Patient Advisory Council (PAC) to add further details on the experience in Tandem VR.

B. SETTING

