- Have a condition that interferes with VR usage, including but not limited to seizures, facial injury precluding safe placement of headset.
- Have a prognosis of hours or actively dying at the time enrollment.
- Patients with motion sickness
- Patients with claustrophobia
- Patients with visual and hearing impairment
- Patients with inability to speak English.

3. Sample Size

n/a

4. Local Number of Participants

The study will recruit 20+ patient and caregiver dyads from Prisma Health Hospice of the Foothills

5. Study-Wide Number of Participants

This is a multi-site study, and we expect to recruit a total of 20+ patient-caregiver dyads from Prisma Health Hospice of the Foothills across the upstate of South Carolina through hospice and bereavement services in Oconee, Pickens, Greenville, and Anderson counties.

6. Recruitment Methods

Prisma Health Institutional Review Board approvals will be obtained for the study.

Participants will be primarily recruited using flyers and word-of-mouth. Research Recruiters (n=10) will be CITI trained, affiliated with, and working alongside with Prisma Health Hospice of the Foothills staff. Recruiters will assist with consenting dyads, launching the intervention, data collection, and offering expert insights on the use of the intervention as a non-pharmacological modality. Ongoing dialogue between the social workers and the research team will allow for continuous improvement in the intervention delivery and offer data on the acceptance of the intervention for hospice patients and caregivers. All information will be explained in a nontechnical fashion and ample time will be available for the participants to ask any questions. This study will recruit a total of 20+ patient-caregiver dyads who will then be screened using the inclusion and exclusion criterion to ensure participant eligibility.

Flyers about the study, word-of-mouth from Research Recruiters.

E. SPECIFICS OF STUDY PROCEDURES

Screening and Pre-intervention

- Enrolled participants will be consented to per approved Prisma Health consent.
- Consented participants will be screened by the research assistant to ensure eligibility of participants, based on inclusion/ exclusion criterion and will complete the Tandem VR Intake form.

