- Eligible participants will meet with the Research Recruiters and baseline data will be collected including demographics. Also, participants will complete Wisconsin Brief Pain Questionnaire (WBQP), Collett-Lester Fear of Death (FOD) scale, and McGill Quality of Life (QOL) scale directly before and after the intervention.
- Research recruiters will meet with participants in the home setting to assist dyads and implement the Tandem VR intervention.
- Upon completion of the intervention, Research Recruiters will collect the Tandem VR equipment and readminister the WBQP, FOD, QOL instruments, and semi-structured interviews.
- Consent from dyads will have been obtained by the Research Recruiters to participate in the Patient Advisory Council (PAC) to work with the researchers on understanding the experience.

Intervention

All procedures completed below will be done on one home visit.

The Tandem VR intervention will be carried out in the patient-caregiver dyad's home setting with the Research Recruiters implementing the experience. Each member of the dyad will initially complete the McGill Quality of Life Questionnaire-E (MQOL-E), Wisconsin Brief Pain Questionnaire (BPQ), and Collet-Lester Fear of Death (FOD) Scale prior to beginning the Tandem VR experience through an electronic medium.

Following completion of the pre-intervention forms, the dyads will be assisted by the Research Recruiter to don the VR HMD. The Research Recruiter will ensure safety for both participants while using the devices. The Research Recruiter will then initiate the Tandem VR experience using the iPad device to synchronize the nature-based scene for viewing. The duration of the experience will be 5-15 minutes.

Upon completion of the Tandem VR intervention, the HMD devices will be removed from the dyad participants. They will then complete the three instruments of the MQOL-E, BPQ, and FOD. Following the completion of the post-intervention documents, the Research Recruiter will conduct the semi-structured interview with the participants. Each participant will be asked the following questions to reflect on their experience:

- Tell us about your experience in Tandem VR?
- What was it like being together in the Tandem VR experience?
- Was there anything about the Tandem VR experience that helped you?
- Was there anything about the Tandem VR experience you feel could be improved?

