- Were there any unusual sensations such as dizziness, lightheadedness, or disorientation while you were in the Tandem VR experience? If so, please explain.

These procedures will be carried out with each dyad for a duration of 8-16 weeks to ensure enough participation in the study. Research Recruiters will also identify participant dyads that can participate in the PAC to discuss the experience with the primary research team.

At this point the study will be completed for the dyads.

The study will recruit 20+ patient-caregiver dyads from Prisma Health Hospice of the Foothills. The participants will be enrolled in the study for 1 intervention with Tandem VR. Each dyad will receive \$20 for participating in the study (a \$10 gift card to the patient and \$10 gift card to the caregiver).

Cleaning and Disinfection of VR -Head Mounted Display (VR- HMD)

As part of a clinical study, virtual reality headsets will need to be reused between patients. At the end of the intervention the VR- HMD will be disinfected. Infection control measures include:

- Hand hygiene will be performed prior to cleaning and disinfection of HMD.
- Headsets that are disinfected will be handled with clean hands to prevent contamination.
- Participants will be instructed to not use headsets if there is a break in their integrity or have visible soiling.

Cleaning of HMD:

Use manufacturer's approved (VRCOVER antibacterial wipes) wipes for removal of all visible bioburden from headset and controller for disinfection.

Disinfection of HMD:

Follow cleaning instructions using disinfection wipes.

The above cleaning protocol has been approved by Prisma Health Infection Prevention.

Participants will continue to follow-up as normal with their physicians at Prisma Health Hospice of the Foothills.

1. Study Timelines

Tandem VR: Synchronized Nature-Based Experiences in Virtual Reality for Hospice Patients and their Caregivers

Table 1 Schedule of Assessments (Study Calendar)

Procedures	Pre-Intervention	Post-Intervention	PAC Meeting (Week 8)
Informed consent	X		
Inclusion/exclusion criteria	X		
Demographics	X		
Cognitive Assessment	X		
McGill Quality of Life Questionnaire-E (MQOL-E)	X	X	
Wisconsin Brief Pain Questionnaire (BPQ)	X	X	
Collett-Lester Fear of Death (FOD) Scale	X	X	
Semi-Structure Questions		X	
Dyads for PAC			X

Timeline of Study

*N_{total} ≥ 20 Patient-Caregiver Dyads

Inclusion Criteria:

- Ability to speaking English

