The risks associated with participation in this study are no greater than those typically encountered in normal day activities. Certain aspects of the participant’s demographics will be collected for this study. Loss of privacy may lead to problems with insurability or social stigmatization. In terms of privacy, participant’s data and associated records will be kept in a secure encrypted, password-protected database. Confidentiality of participant information and study activities will also be emphasized to all research personnel. These risks are considered to be minimal and are addressed in the protocol and consent form.

Participants may develop VR-related symptoms such as motion sickness effect, nausea, and headache, often referred to as cybersickness. Measures will be taken to assess if any symptoms of cybersickness occur and discontinue the intervention immediately. The greatest risk is the possible release of your personal health information. The study records are considered confidential, but absolute confidentiality cannot be guaranteed. This study may result in presentations and publications, but steps will be taken to make sure patient data is deidentified. Some of the questions in the surveys/questionnaires are personal and may be upsetting to some participants. The study doctor or staff will be available to discuss these questions should you have a concern or problem. You do not have to answer any questions that you do not want to answer.

In case patients or patient caregivers become emotional during the Tandem VR experience, a Hospice care on-call social worker will be providing real-time and immediate counseling.

2. Potential Benefits to Participants

We expect that this study will demonstrate Tandem VR is an effective non-pharmacologic treatment for the management of physiological distress of patient-caregiver dyads; moreover, we expect Tandem VR will be feasibly and safely deployed in home settings. The expected outcomes from this study include reduction in pain, reduced fear of death and improved quality of life for participants. This intervention is also likely to show improved interactions between patient-caregiver dyads through the imagery used in Tandem VR. The outcomes from this study will be used

to optimize Tandem VR to user satisfaction. The results will also be used to inform and refine future design guidelines and practices for the implementation of Tandem VR for patient-caregiver dyads in the hospice home setting.

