**For all three quantitative measures means and standard deviations will be calculated to summarise the results.**

4. Open-ended questions will be asked to determine the perceived benefit and value of the Tandem VR post-intervention with patient-caregiver dyads.

**Themes will be derived from the responses provided by the dyads, providing rich insights on the intervention to inform the researchers of individual experiences.**

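### Safe use at home is an objective with a favourable conclusion expected, but the planned analysis counts neither symptoms nor early stops, so no rate will stand behind that conclusion

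*Protocol*

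**What the plan says.** **Objective and expectation.** Protocol III.B states: "The investigators will also assess acceptability and safety of Tandem VR at home". It goes on: "moreover, we expect Tandem VR will be acceptable and safely deployed in home settings". Section III.A and the benefits section (V.A.2) carry similar expectations.

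**Data on symptoms.** The interview in IV.E is put to everyone: "Each participant will be asked the following questions to reflect on their experience". One of its five questions is "Were there any unusual sensations such as dizziness, lightheadedness, or disorientation while you were in the Tandem VR experience". III.B adds direct observation and audio recording, and the data management section (IV.E.5) stores field notes and transcribed answers in a spreadsheet.

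**Named risks and stops.** V.A.1 says: "Participants may develop VR-related symptoms such as motion sickness effect, nausea, and headache, often referred to as cybersickness". It continues: "Measures will be taken to assess if any symptoms of cybersickness occur and discontinue the intervention immediately".

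**Outcomes and analysis.** Protocol IV.E.3 and the SAP list the same outcomes: three scales (MQOL-E, BPQ, Collett-Lester), open-ended questions to dyads on benefit and value, and interviews with hospice staff and recruiters. The SAP gives means and standard deviations for the three scales. For the open-ended questions it says: "Themes will be derived from the responses provided by the dyads".

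**Size.** Section IV.D.4: "The study will recruit 20+ patient and caregiver dyads from Prisma Health Hospice of the Foothills". The sample size section is marked not applicable.

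**The concern.** The protocol sets out to assess safe use at home and says in advance what it expects to find. A reader of the final report will want to know how many people felt unwell, how many sessions were stopped and how many were completed. No listed outcome or planned summary supplies those numbers, and no criterion for safe or acceptable is given.

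The results are meant to inform best practice and later, larger studies. A theme saying that participants tolerated the session well could then be carried forward as evidence of safety, while a material symptom rate remained compatible with the data. The people most informative about safety, those who stop, are also the ones whose data the plan secures least clearly.

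**Working it through.** **1. Trace the objective to an analysis.**

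| Quantity needed | Collected? | Listed outcome? | Planned analysis |
|---|---|---|---|
| Symptoms | Yes: one open question to each participant, plus observation and field notes | Only within the open-ended questions | Themes |
| Early stop | Foreseen in V.A.1; no recording step described | No | None |
| Session completed | Not described | No | None |
| Dyad acceptability | Yes: open-ended questions | Primary outcome 4, qualitative | Themes |
| Staff acceptance | Yes: staff and recruiter interviews | Secondary outcome | Insights, no measure given |

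Table 1 has rows for the three scales and the semi-structured questions, but none for symptoms, adverse events or stops. The protocol's statistical section (IV.E.7) adds pre/post tests and triangulation, and no counts.

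**2. Compare the question with the risks.** V.A.1 names motion sickness, nausea and headache. The question prompts for dizziness, lightheadedness and disorientation. Its wording is open enough for someone to volunteer nausea or headache, but neither is prompted, so a count from this question alone could run low.

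**3. Follow a participant who stops.** IV.E places the repeat questionnaires and the interview after the intervention has been completed. V.A.1 foresees sessions being discontinued. Neither place says whether a person who stops is interviewed or how the stop is recorded. As an illustration (my assumption, not a figure in the documents), suppose 20 patients start, 2 stop with symptoms and are not interviewed, and the other 18 report nothing. The interviews show 0 of 18. Among all who started the figure is 2/20 = 10%, exact 95% CI 1.2% to 31.7%.

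**4. What counting would deliver.** The documents give no safety rate or precision target, so there is no figure to reproduce. With zero events in n people, the exact two-sided 95% upper limit is 1 − 0.025^(1/n).

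- n = 20 (patients, or caregivers, at the planned minimum): 1 − 0.025^(1/20) = 16.8%
- n = 40 (both roles pooled): 1 − 0.025^(1/40) = 8.8%

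The n = 40 figure treats the two members of a dyad as independent, although they share one synchronised session. If their outcomes always agreed, 40 people would carry the information of 20 and the limit would return to 16.8%.

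The gift-card budget in IV.B.1 ($520 at $20 per dyad, so 520/20 = 26 dyads) suggests that slightly more dyads are possible. The limits would then be 13.2% (n = 26) and 6.8% (n = 52, again assuming independence).

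**5. Chance of seeing no event at all**, (1 − p)^n, for assumed true rates p that are not in the documents:

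| True rate | n = 20 | n = 40 (independent) |
|---|---|---|
| 2% | 66.8% | 44.6% |
| 5% | 35.8% | 12.9% |
| 10% | 12.2% | 1.5% |
| 20% | 1.2% | about 0% |

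**6. Completion.** If 18 of 20 completed, the exact 95% CI is 68% to 99%. If 20 of 20 did, it is 83% to 100%.

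**The case against.** A reader might infer that the trial cannot answer the safety and acceptability question at all. The documents do not support that. Every participant is asked about unusual sensations, the interview has its own row in Table 1, and observation, recording and field notes are planned. The answers exist person by person and could be tallied afterwards. What is missing is a plan to count them.

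A reader might also infer that there is no acceptability outcome for dyads. That too goes too far. Primary outcome 4 asks dyads about benefit and value, and the interview asks what helped and what could be improved. In a declared mixed-methods study this is a recognisable qualitative acceptability outcome. The formal acceptance aim concerns hospice teams, and the secondary outcome addresses it.

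Three further points have weight. Safety is in the objectives text of III.B but not among the two numbered aims in III.A, and the expected conclusion is an expectation, not a test. The limits in step 4 are a consequence of sample size and would remain after the fix; they bound what may be claimed and do not measure the omission. And the spreadsheet's variable list and the interview guide in Appendix D were not in the text available to me. Absence is therefore established for the outcome lists, Table 1 and the SAP, but not for every data form.

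What survives is narrower: an analysis of dyads' answers that yields only themes produces no rate, and the expected statement about safe deployment needs one.

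**Conclusion.** The point holds in this limited form. Safe use at home is an objective with a favourable conclusion expected, yet symptoms reach the analysis only as themes from one open question, and early stops reach it not at all. Acceptability to dyads is covered, but only qualitatively. The planned analysis gives no rate behind a claim of safe deployment, and those who stop may go unrecorded. It cannot be said that they will be lost; the documents leave this open.

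After the fix, zero events would still be compatible with a true rate of up to 16.8% in 20 patients or in 20 caregivers. The pooled 8.8% rests on independence within dyads and should not be the headline. These figures assume the planned minimum of 20 dyads, with everyone who starts a session counted. The change is worth making because it is inexpensive and the study's results are intended for reuse.

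**What to change.** Add to the SAP, separately for patients and for caregivers, the number and percentage with an exact 95% CI of participants:

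- (a) reporting any symptom to the unusual-sensations question, with the prompt extended to the nausea and headache that the protocol names as risks;
- (b) whose session was stopped early, with the reason;
- (c) who completed the session.

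The denominator is everyone who starts a session.

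Reconcile V.A.1 with the session procedures in IV.E and with Table 1, so that a stop is recorded when it happens and the symptom question is also put to those who stop. This concerns recording only and leaves the handling of symptoms as it is.

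Report (c) beside the acceptability themes from primary outcome 4. A count of people who declined is not recommended: recruitment is by flyers and word of mouth, no log of approaches is described, and declining research is not the same as finding VR unacceptable.

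Replace the expected conclusion of safe deployment in III.A, III.B and V.A.2 with a commitment to report the observed rate and its upper limit, and say that the sample allows description only.

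Cost: a few extra data fields, a small change to one interview prompt, one table, and a more modest claim.
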